Stopping Rules	
For Phase 1 dose escalation, a dose level will be considered unacceptable if 2 or more patients of the 6 eligible patients experience a DLT (see below). Should all 7 patients in the Cohort be analyzable for adverse events, only the first 6 will be considered in the determination of DLTs. A patient who misses more than 7 days of PLX3397 administration during the 7-week dosing period of Cycle 1 (4 weeks) and Cycle 2 (3 weeks) for reasons other than having had a DLT will be replaced. If 2 or more patients in a Cohort experience a DLT, no patients in the Cohort will be replaced. If >2 of the first 6 patients in Dose Level -2 (400 mg/day of PLX3397) experience a protocol-defined DLT, the combination will be considered too toxic and the study will be discontinued.
 
After approximately 50% of the planned Phase 2 patients have completed their concurrent radiation therapy, an overall interim safety summary will be reviewed by the Medical Monitor and principal investigators to ensure that the potential clinical benefit outweighs the observed clinical risk to date. If the safety observations do not warrant continued enrolment, the study will be discontinued.

PK Parameters	For the Phase 1b portion of the study, a partial AUC ( $AUC_{0-6}$ ) will be calculated using samples collected from C1D8 (pre-temozolomide) and C1D15 (concurrent temozolomide). Values for $C_{max}$ and $T_{max}$ will be determined from the concentration-time profile.
PD Parameters	CD14/16 mononuclear cell counts, CSF-1, and biomarkers of kinase inhibition and myeloid cell recruitment. Surgical tissue will be evaluated for MGMT methylation, CSF-1, CSF1R, tumor-associated macrophages, and other prognostic biomarkers in order to correlate with treatment response and inform enrichment strategies for subsequent studies in this patient population. If the MGMT methylation status of the study population differs from that observed in the RTOG 0525 study, the benchmark mPFS of 5.5 months will be adjusted appropriately.
Endpoints	
Primary: Median PFS by RANO criteria
 
Secondary: Safety, OS, PK, correlative imaging
 
Exploratory: PD biomarkers

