### **21.2 Sample Size and Power**

For the primary endpoint of median PFS, based on a one-sided log rank test with a significance level of 0.1 and power of 80%, 22 events (death or progression) in approximately 31 patients would be required to detect a 50% relative hazard reduction in progression-free survival due to the addition of PLX3397 compared to the recent historical control median PFS of 5.5 months (RTOG 0525). Assuming a ~30% rate of non-evaluability, approximately 37 patients are planned to be enrolled in the Phase 2 portion of the study, which when combined with the 7 patients treated at that dose level in the Phase 1 portion of the study will yield approximately 44 patients.

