#### 21.4 Efficacy Analysis

Response to treatment will be evaluated using the Response Assessment in Neuro-Oncology (RANO) criteria (Wen 2010). The response criteria are summarized in Attachment 3. All patients who are eligible for efficacy analyses will be evaluable for PFS, calculated for each subject as the number of days from the first day of treatment (C1D1) to the date of the first documented disease progression or date of death, whichever occurs first. The Kaplan-Meier method will be used to estimate the median PFS.

Statistical modeling will be used to match the experimental group to the RTOG 0525 historical group for expected prognosis based on both clinical and molecular factors, importantly the level of MGMT methylation in the tumor tissue.

For each subject with a response to therapy, duration of response will be calculated. The duration of response is defined as number of days from the date of initial response to the date of first documented disease progression or death, whichever occurs first. The Kaplan-Meier method will be used to estimate median duration of response. In the event no disease progression or death is documented prior to study termination, analysis cutoff, or the start of confounding anticancer therapy, PFS and duration of response will be censored at the date of last evaluable tumor assessments. The median duration will be compared to the historical control PFS of 5.5 months. The secondary endpoint of OS will be analyzed in a similar fashion.

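### The null value of the primary PFS test is not fixed: the 5.5-month benchmark will move with MGMT status under no written rule, so the one-sided 0.10 is not assured

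*Combined protocol and SAP*

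**What the plan says.** Sections 9.0 and 21.1.2 give Phase 2 one primary objective: comparing median PFS with a historical control. Three places describe the comparator.

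- **Section 21.2 and the synopsis row on statistical considerations.** The design is "based on a one-sided log rank test with a significance level of 0.1 and power of 80" percent, and "22 events (death or progression) in approximately 31 patients would be required" to "detect a 50% relative hazard reduction in progression-free survival". The comparator is 5.5 months from RTOG 0525, with no mention of adjustment.
- **Synopsis, PD parameters.** "If the MGMT methylation status of the study population differs from that observed in the RTOG 0525 study", then "the benchmark mPFS of 5.5 months will be adjusted appropriately".
- **Section 21.4.** "Statistical modeling will be used to match the experimental group to the RTOG 0525 historical group for expected prognosis", on clinical and molecular factors, with MGMT methylation singled out. A later sentence reads: "The median duration will be compared to the historical control PFS of 5.5 months". It follows text on both PFS and duration of response, so what it compares is unclear.

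The synopsis clause does not say how large a difference triggers the adjustment, which MGMT cut-point applies, what the RTOG 0525 PFS is by MGMT stratum, what formula is used, when it is applied or by whom. Section 21.4 names no model. The only further analysis plan announced is for PK (Section 21.6).

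**The concern.** In a single-arm trial the historical value is the null hypothesis. If it can move and the size of the move is unwritten, the design alpha does not describe the test that will be run. The study's MGMT mix can be known only once patients are enrolled and tested. The trial is open label (Section 10.1), and nothing requires the adjustment to be settled before PFS is looked at. Section 21.7.2 gives the historical comparison as a reason for requiring surgical tissue, so the clause is likely to be used. At stake is whether the trial is declared positive: a half-month change in the benchmark moves the success bar by more than half a month.

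**Working it through.** **1. The plan's own figure.** Inputs from Section 21.2: one-sided alpha 0.10, power 80%, 22 events, about 31 patients, about 30% non-evaluable. For a one-sample log-rank against a known null (square-root scale), expected events under the null are E0 = [(1.282 + 0.842) / (2(1 − √HR))]², and observed events are HR × E0.

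- HR 2/3 (median 1.5 × 5.5 = 8.25 months): E0 = 33.5 and 22.3 observed events. This matches 22; power at 22 events is 79.6%.
- HR 0.5, the literal hazard reduction: 6.6 events, no match. Two-sample 1:1 formulas give 38 (Schoenfeld) or 41 (Freedman), also no match.
- Non-evaluability: 31 / 0.70 = 44.3, against 44 planned.

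So the event count comes from a test that treats the benchmark as a known constant. It has no term for adjustment, and the 0.10 belongs to that unadjusted test.

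**2. Sensitivity to the benchmark.** With 22 events and exponential PFS, 2 × 22 × (estimated median / true median) follows a chi-square with 44 degrees of freedom, whose 90th percentile is 56.37. The success bar is therefore benchmark × 56.37/44 = benchmark × 1.281. If the true no-effect median is m and benchmark b is used, type I error is P(χ²₄₄ > 56.37 × b/m).

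| Benchmark (months) | Success bar (months) | Type I error if true null is 5.5 | Power at 8.25 |
|---|---|---|---|
| 5.0 | 6.41 | 21.1% | 85.7% |
| 5.5 | 7.05 | 10.0% | 74.2% |
| 6.0 | 7.69 | 4.2% | 60.1% |
| 6.5 | 8.33 | 1.5% | 45.4% |

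For example, b = 5.0 and m = 5.5 give a threshold of 56.37 × 5.0/5.5 = 51.2, exceeded with probability 0.211. An estimated median between 6.41 and 7.69 months passes or fails according to a half-month shift one way or the other.

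Leaving 5.5 alone is not safe either. If the MGMT mix makes the true null 6.0, the threshold is 56.37 × 5.5/6.0 = 51.7 and type I error is 19.9%; at 6.5 it is 32.5%.

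**3. What a locked rule would do.** The documents give no MGMT figures, so these inputs are assumptions: 30–40% methylated historically, methylated-to-unmethylated PFS hazard ratio 0.5–0.7, and a study share up to 20 points higher or lower. PFS is a mixture of two exponentials with overall median 5.5 months. Near the planned event count, under no effect:

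- fixed 5.5 months: type I error about 2% to 27%;
- a pre-written MGMT-mix benchmark, or expected hazards by MGMT stratum: near 9%.

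A second simulation used the exact test, 31 patients, 22 events, 30% methylated historically, methylated median 1.5 to 2 times unmethylated, and a study share of 30% to 50%. It gave 10.4% to 31.2% for fixed 5.5, 10.0% to 12.1% for the pre-written mix benchmark and 9.6% to 10.4% for the stratified test.

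**The case against.** Much can be said for the plan.

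- **MGMT is a baseline factor.** It is measured on surgical tissue identified at screening. Treatment cannot alter it, and it can be tabulated without PFS. A reader might infer that the null will be chosen after outcomes are seen. The documents do not say so: they give no timing, and the fair statement is that nothing requires the rule to be locked first.
- **The clause is conditional, not optional.** The benchmark will be adjusted if MGMT status differs.
- **Three rival primary analyses is an overcount.** Section 21.2 must use some planning value, and the synopsis clause and the matching sentence in Section 21.4 can be read as one intention. What remains is a fixed and an adjusted comparison, with no rule choosing between them.
- **Adjustment is not the fault.** The 2% to 27% range is the error of the unadjusted test, so it supports adjusting. Nor does picking the most favourable of the three analyses add much once each is properly specified: 11.7% to 31.2% in the second simulation, against 10.4% to 31.2% for fixed 5.5 alone.
- **A higher error should not be headlined.** With 44 patients followed for 18 months, the fixed test can reach about 42%, but only at the most extreme assumed inputs. Part of that comes from testing mixture data against a single exponential; against the historical mixture curve the maximum is 31%.

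All of this stands. It does not supply the missing trigger, formula, timing or designation of the primary comparison.

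**Conclusion.** The point holds as a specification fault in the primary test: the null value is not fixed, and the stated 0.10 is not assured for whichever comparison is finally made. A half-month error in the benchmark, in the direction that lowers the bar, roughly doubles type I error, whether it comes from a shift that was not warranted (21%) or from a warranted shift not made (20%). An unwarranted upward shift cuts it to about 4% and costs power. These figures rest on exponential PFS and 22 events. The comparison of fixed and locked rules also rests on assumed MGMT inputs. Most of the gain comes from locking one MGMT-adjusted rule; stratum-specific hazards are a modest further improvement over a written mix formula.

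**What to change.** Before any Phase 2 PFS review, replace "the benchmark mPFS of 5.5 months will be adjusted appropriately" with one locked primary test.

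- **Preferred:** a one-sample log-rank in which each patient's expected hazard comes from the historical PFS curve for that patient's MGMT stratum, with the assay cut-point stated. Patients with unknown MGMT take the overall curve.
- **If stratum curves on a comparable time origin are unavailable** (PFS here starts at C1D1): a written formula giving the benchmark as a function of the observed MGMT mix.
- **Supportive only:** the fixed 5.5-month comparison and any wider model-based matching.
- **Restate** events and power for the chosen test. That means settling whether the target is a 50% hazard reduction or the median of about 8 months in Section 10.5, since 5.5/8 is a hazard ratio of 0.69.

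The cost is analysis-plan wording plus obtaining historical MGMT-specific PFS. MGMT testing is already planned for all patients. The documents do not show that suitable historical curves exist, but any MGMT adjustment needs such data. Patients with unknown MGMT will not be adjusted for it.

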**TRIAL FLOW CHART – Phase 1b Dose Escalation Phase**

STUDY DAY▶	Screening	4 Week Cycle				3 Week Cycle				4 Week Recovery Period				4 Week Cycle		4 Week Cycle	End of Rx
	Day -21 to -1	C1D1 (-2d)	C1D8 ±2d	C1D15 ±2d	C1D22 ±2d	C2D1 ±2d	C2D8 ±2d	C2D15 ±2d	C2D22  ±2d	RPD 1 ±2d	RPD 8 ±2d	RPD 15 ±2d	RPD 22 ±2d	C3D1  ±7d	C3D22 ±2d	Day 22 of Cycle 4+  ± 7d	
EVENT ▼																	
Informed Consent	X																
Medical History	X																
Height	X																
Weight	X	X				X			X					X	X	X	X
Vital Signs	X	X	X	X		X			X					X	X	X	X
Physical Exam 	X	X	X	X		X			X					X	X	X	X
ECG 	X					X											X
Chem	X	X		X		X			X					X	X	X	X
Hematology 	X	X	X	X	X	X	X	X	X		X			X	X	X	X
Plasma for PK 		X	X	X													
Plasma PD Biomarkers 		X	X			X								X			
Whole Blood for CD14/16		X	X														
Serum Pregnancy Test 	X																X
Surgical Specimen for PD	X																
Karnofsky Performance Status	X	X				X			X					X	X	X	X
MDA Symptom Inventory		X							X					X	X	X	X
MRI Brain Scan 	X													X		X	
Study Drug Dosing 		X-----X												X-----X			
Study Drug Compliance		X	X	X		X			X						X	X	X
Radiation Therapy			X-----X														
Temozolomide 			X-----X												X 		
Concomitant Medications	X	X	X	X		X			X					X	X	X	X
Adverse Events 		X	X	X		X			X					X	X	X	X

EXPLANATION OF SUPERSCRIPTS:

1. The cycle length for Cycle 2 is 3 weeks, to complete the 6 weeks total of radiation therapy.
2. C3D1 is the first dose of the adjuvant retreatment with temozolomide and study drug, beginning approximately 4 weeks after the completion of RT.
3. If well tolerated and no tumor progression; clinic visits, laboratories every 4 weeks with radiographic assessment performed every 8 weeks (every 2 cycles).
4. Complete physical exam (including neurological exam) at Screening, and neurological exam plus symptom-directed physical exam subsequently.
5. Hematology: CBC, differential count, platelet count.
6. On C1D1, obtained pre-dose. On C1D8 and C1D15, obtained pre-dose, 1, 2, 4, and 6 hours post-dose.
7. Blood samples for circulating CSF-1 and biomarkers of kinase inhibition and myeloid cell recruitment will be obtained pre-dose on C1D1, C1D8, C2D1, and C3D1. CD14/16 mononuclear cell counts will be obtained pre-dose on C1D1 and C1D8. Samples will be collected and processed by LabCorp according to the study-specific laboratory manual. LabCorp will perform the MGMT analyses.
8. For women of child-bearing potential. At screening, obtained within 14 days of the first dose of study drug.
9. A diagnostic contrast-enhanced MRI or CT scan of the brain must be performed preoperatively and postoperatively prior to the initiation of radiotherapy, i.e. within 28 days (14 days preferred) prior to study drug administration (C1D1). Patients unable to undergo MR imaging because of non-compatible devices can be enrolled, provided pre- and post-operative contrast-enhanced CT scans are obtained and are of sufficient quality.
10. Two PLX3397 BID administration schedules, 7 days/week vs. 5 days/week (M-F) will be explored for Cycle 1 and 2. PLX3397 will be administered BID 7 days/week for Cycle 3 and subsequent cycles until disease progression disease or unacceptable toxicity.
11. Temozolomide is taken orally once daily for 5 days followed by 23 days without treatment for each cycle beginning with C3D1 for up to 12 cycles.
12. Monitored throughout the study via safety assessments, observation, and participant reporting.
13. Standard 12-lead ECG with QTcF calculation. Fridericia's formula is required.  $QTcF = (QT)^3 \sqrt{(RR)}$

**TRIAL FLOW CHART – Phase 2**

STUDY DAY▶	Screening	4 Week Cycle			3 Week Cycle		4 Week Recovery Period	4 Week Cycle		4 Week Cycle	End of Rx
	Day -21 to -1	C1D1 (-2d)	C1D8 ±2d	C1D15 ±2d	C2D1 ±2d	C2D22  ±2d		C3D1  ±7d	C3D22 ±2d	Day 22 of Cycle 4+  ±7d	
EVENT ▼											
Informed Consent	X										
Medical History	X										
Height	X										
Weight	X	X			X	X		X	X	X	X
Vital Signs 	X	X	X		X	X		X	X	X	X
Physical Exam 	X	X	X		X	X		X	X	X	X
ECG 	X				X						X
Hem, Chem 	X	X	X	X	X	X		X	X	X	X
Plasma PD Biomarkers 		X	X		X			X			
Whole Blood for CD14/16		X	X								
Serum Pregnancy Test 	X										X
Surgical Specimen for PD	X										
Karnofsky Performance Status 	X	X			X	X		X	X	X	X
MDA Symptom Inventory		X				X		X	X	X	X
MRI Brain Scan 	X							X		X	
Study Drug Dosing 		X-----X						X-----X			
Study Drug Compliance 		X	X	X	X	X			X	X	X
Radiation Therapy			X-----X								
Temozolomide 			X-----X					X 			
Concomitant Medications 	X	X	X	X	X	X		X	X	X	X
Adverse Events 		X	X	X	X	X		X	X	X	X

EXPLANATION OF SUPERSCRIPTS:

1. The cycle length for Cycle 2 is 3 weeks, to complete the 6 weeks total of radiation therapy.
2. C3D1 is the first dose of the adjuvant retreatment with temozolomide and study drug, beginning 4 weeks after the completion of RT.
3. If well tolerated and no tumor progression; clinic visits, laboratories every 4 weeks with radiographic assessment performed every 8 weeks (every 2 cycles)
4. Complete physical exam (including neurological exam) at Screening and neurological exam plus symptom-directed physical exam subsequently.
5. Blood samples for circulating CSF-1 and biomarkers of kinase inhibition and myeloid cell recruitment will be obtained pre-dose on C1D1, C1D8, C2D1, and C3D1. CD14/16 mononuclear cell counts will be obtained pre-dose on C1D1 and C1D8. Samples will be collected and processed by LabCorp according to the study-specific laboratory manual. LabCorp will perform the MGMT analyses.
6. For women of child-bearing potential. At screening, obtained within 14 days of the first dose of study drug.

## 7.0 INTRODUCTION

### 7.1 Background

Kinases play a ubiquitous role in the signaling pathways for proliferation, metastasis, and survival of most tumor types. PLX3397 is a potent and selective inhibitor of Fms (the receptor for colony stimulating factor 1, CSF1, also known as macrophage-colony stimulating factor, M-CSF), Kit (the receptor for stem cell factor, SCF) and oncogenic Flt3 (the receptor for Flt3 ligand). Fms and Kit are regulators of key components of the tumor microenvironment, namely microglia, macrophages, osteoclasts, and mast cells.

PLX3397 is a novel, orally active, small molecule inhibitor that targets Fms, Kit and oncogenic Flt3, but remains highly selective versus other kinases. The potent inhibition of these three kinases can be exploited to attack tumors via different mechanisms: 1) directly inhibiting oncogenic drivers such as oncogenic Kit and Flt3 mutant proteins, 2) inhibiting paracrine loops between stromal cells and tumors, 3) blocking migration and angiogenesis, and 4) disrupting osteolytic metastases. The inhibition of these activities by PLX3397 has been characterized in cellular and in vivo assays. The pharmacologic efficacy demonstrated to date and the therapeutic promise support further development of PLX3397 as an anti-cancer therapeutic.

Glioblastoma (GBM) is the most frequent brain tumor, accounting for approximately 12% to 15% of all brain tumors. The peak incidence occurs between the ages of 45 and 70 years. For patients with glioblastoma (World Health Organization grade IV), there is no cure, and standard local treatment of surgery plus radiotherapy ± chemotherapy is associated with only a modest improvement in outcome parameters. According to the National Cancer Institute, patients with brain tumors that are either infrequently curable or unresectable should be considered candidates for clinical trials that evaluate new drugs and biological response modifiers following radiation therapy.

The rationale for testing the Fms/Kit inhibitor PLX3397 in GBM is provided by the following scientific evidence:

1. Infiltrating microglia are associated with a markedly reduced survival ([Komohara 2008](#))
2. A mesenchymal signature also predicts reduced survival in GBM ([Phillips 2006](#)). This signature includes well-described microglial markers such as CD68, PTPRC, TNF, and NF1 mutations ([Verhaak 2010](#))
3. A microglial-weakening polymorphism (V249I) is associated with increased survival ([Rodero 2008](#))
4. Many glioma cell lines established from patient samples express high concentrations of ligands for Fms (CSF-1 and IL-34) or Kit (SCF). This secretion in turn attracts and activates surrounding microglia, which facilitate tumor invasion via elaboration of proteases such as MT1-MMP and MMP2.
5. Depletion of microglia in orthotopic GBM models reduces tumor burden and spread.
6. Macrophages and microglial cells are recruited by tumor cells as a resistance mechanism in response to radiotherapy ([Ahn 2010](#)).

In pharmacology studies, PLX3397 (1  $\mu$ M) has been shown to markedly reduce the invasion of GL261 glioblastoma cells when co-cultured with microglia in a matrigel invasion assay. Furthermore, PLX3397 administered by chow for 10 days resulted in a significant reduction ( $p=0.029$ ) in tumor growth in the 9L Fisher rat glioma model. Also, PLX3397 avidly crosses into the CNS of rats (similar to the positive brain penetration control compound, antipyrine) and is not a substrate for active transport, suggesting that PLX3397 will reach GBM tumors and surrounding stromal tissue within the CNS even with an intact blood brain barrier. Finally, PLX3397 has shown a synergistic effect when combined with radiation therapy in pharmacology models of prostate cancer and GBM.

## 7.2 Pharmacodynamics

In brief, biochemical data support Fms, Kit and oncogenic Flt3 as key targets of PLX3397. Consequently, proliferation of cell lines that alternatively depend on CSF-1 or SCF ligands, or are driven by Flt3 that is oncogenically activated by internal tandem duplications (Flt3-ITD), is inhibited by PLX3397 at  $IC_{50}$  values below 1  $\mu$ M. Furthermore, CSF-1-induced autophosphorylation of Fms and SCF-induced autophosphorylation of Kit are potently inhibited by PLX3397. By contrast, both autophosphorylation and proliferation of cells induced by addition of Flt3 ligand are only weakly inhibited by PLX3397, suggesting preferential inhibition of the oncogenically-activated Flt3 kinase. Finally, the RANK-L and CSF-1-dependent differentiation of osteoclast precursors is also potently inhibited by PLX3397. These in vitro effects translated to effects in a variety of in vivo models designed to test the effects of PLX3397 on Fms-dependent proliferation, Fms-dependent osteoclast differentiation, and Flt3-ITD dependent tumor growth.

### 7.2.1 In Vitro Pharmacodynamics

PLX3397 shows significant selectivity versus a panel of over 200 kinases. Fms, Kit, and mutant Flt3-ITD appear to be the most sensitive target kinases, with  $IC_{50}$  values of 17, 12, and 9 nM, respectively (see [Table 1](#)).

**Table 1:  $IC_{50}$  Values of PLX3397 Against Selected Kinases**

Kinase	Fms	Kit	Flt3-ITD	Kdr	Lck	Flt1	TrkC
PLX3397	17 nM	12 nM	9 nM	213 nM	860 nM	880 nM	890 nM

Kdr kinase activity is only modestly affected, and other kinases tested are even less sensitive to PLX3397. While physiologic effects due to the inhibition of Fms and Kit are expected, the selectivity of PLX3397 suggests that minimal off-target effects should be observed. When screened against a broad panel of additional kinases,  $IC_{50}$  values were  $>1$   $\mu$ M for all, with the majority  $>10$   $\mu$ M.

PLX3397 also demonstrated negligible activity in a standard Novascreen panel. This is a screen for off-target activity against a broad array of 71 targets in 8 families (Neurotransmitter-related,

Steroids, Ion Channels, Nitric Oxide, Prostaglandins, Growth Factors, Brain/Gut Peptides, and Enzymes). At a serum-free concentration of 10  $\mu\text{M}$  of PLX3397, all results were within 40% of Baseline, indicating no relevant off-target activity.

M-NFS-60 cells and BAC1.2F5 cells are mouse cell lines that require CSF-1 to proliferate, and Mo7E cells are human cells that require SCF to proliferate. The ligand dependent proliferation of these cells is inhibited by PLX3397 with  $\text{IC}_{50}$  values of 0.33, 0.23 and 0.31  $\mu\text{M}$ , respectively. In THP-1 cells, Fms autophosphorylation induced by CSF-1 can be inhibited by 7 nM concentrations of PLX3397. By contrast, in RS4;11 cells, Flt3 autophosphorylation can be induced by Flt3 ligand and this autophosphorylation requires high levels of PLX3397 (1500 nM) for inhibition, suggesting that PLX3397 binds only weakly to unactivated Flt3. On the other hand, proliferation of MV4-11 cells (that express Flt3-ITD) is potently inhibited by PLX3397 with an  $\text{IC}_{50}$  value of 26 nM. Finally, human osteoclast precursor cells can be induced to differentiate into mature osteoclasts by the combination of RANK-L and CSF-1. PLX3397 inhibits this osteoclast differentiation with an  $\text{IC}_{50}$  value of 33 nM.

